## **Outcomes**

The *primary outcome measure* will be changes in the *one repetition maximum (IRM) isometric lingual pressures* measured at the front and back sensors of the device. Secondary outcomes include *bolus flow durational measurements* taken from videofluoroscopic recordings, *swallowing pressures, SWAL-QOL scores, and FOIS scores*. In addition, we will compare the *number of pneumonia diagnoses* for community, hospital-acquired, and aspiration pneumonia for the same period of time prior to enrollment and following completion of the study (up to nine months). We also will track the *number of hospital re-admissions* for the same period of time prior to enrollment and following completion (up to 9 months). Treatment compliance also will be tracked within the SwallowStrong® device and will serve as a covariate in statistical analyses.

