## **Intervention**

Participants who meet criteria for dysphagia on the videofluoroscopic swallowing examination will be randomly assigned into one of two groups: 1) a control group that will be receiving compensatory treatments only or 2) 12-week DF I-PRO therapy *plus* compensatory treatments, such as thickened liquids and/or postural strategies during natural swallowing activities for 12 weeks. Patients will be enrolled and trained in DF I-PRO therapy by [name] who regularly uses the SwallowSTRONG®-facilitated I-PRO therapy in clinical practice or a UW Voice and Swallowing clinician involved in this study who has been adequately trained in DF I-PRO therapy. Regardless of the treatment group to which a subject is randomized, they will be evaluated in the hospital at baseline and 8-week time points. If a patient in either group no longer meets criteria for dysphagia (Penetration-Aspiration Scale score of 3 or higher OR a rating of 2 on the Residue scale in any location) on the 8-week videofluoroscopic swallowing examination, s/he will no longer continue participation in the study. If a patient in either group remains dysphagic at the 8-week visit, s/he will continue participation in the study through the 12-week assessment point. [name] or a UW Voice and Swallowing clinician will conduct the 8 and 12 week assessments.

**Group 1: Compensatory treatments only:** This group will receive standard swallowing intervention, which is identified by the SLP as appropriate to treat the patient's dysphagia and is common clinical practice. This group is not receiving experimental therapy. Their therapy may include: 1) modifying the foods the subject eats or the fluids s/he drinks; 2) changing his/her posture when eating or drinking (for example, by a simple chin tuck) or using a swallowing maneuver while eating or drinking; 3) having him/her eat more slowly or in a quiet environment to make swallowing easier and safer; or 4) performing range of motion or vocal exercises for

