swallowing or speech. Any progressive strengthening regimens or any type of lingual strengthening protocols specifically will be delayed until subjects have completed participation in this study in order to eliminate confounding influences on outcomes. No subjects will be at risk due to this delay as compensatory approaches mentioned above will be used and other strengthening regimens do not have enough evidence to support their inclusion in standard of care. Weekly check-in phone calls will be scheduled throughout the subjects' participation in the study.

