**Figure 1**

## **Visits**

**Baseline visit only:**

After the informed consent process has been completed but prior to videofluoroscopic examination of swallowing, each participant will complete a medical history questionnaire to ensure they meet inclusion/exclusion criteria. This questionnaire will include items related to current medical status, medical history, and medication usage. UW medical records also will be referenced to ensure the subject's eligibility for participation. As part of this screening, patients will undergo a urine pregnancy test to ensure they are not pregnant prior to participation. The Mini-Mental Status Examination (MMSE) will be administered only at baseline as a common examination of cognitive functioning. In addition, the Barthel index will be administered to assess severity of impairments in activities of daily living. For each patient, a form with demographics as well as a medication list will be filled out. These questionnaires and tests will take approximately 45 minutes to complete. For those subjects randomly assigned to Group 2, during this baseline visit, it also will take approximately 30 minutes to train the participant on how to do and record the exercises properly. In addition to the consent process and these procedures that will occur only at the baseline visit, the procedures described below will also be completed at this visit. The entire baseline visit will last about 2.5 hours. For the baseline visit and 8 week visit, videofluoroscopic examination of swallowing will need to be completed before the other procedures outline below as the outcome of that examination will determine the patient's continued participation in the study. If s/he does not meet criteria for dysphagia on the videofluoroscopic swallowing exam, s/he will either not be randomized to a study group (at baseline visit) or will not continue participation past the 8 week point (if dysphagia has resolved).

*Measures at each assessment point (baseline, 8 weeks, and 12 weeks):* The 8 week and 12 week visits will last about 90 minutes per session. The study includes up to 3 sessions which will require up to 7 hours in total. In addition if in Group 2, participation in the home exercises will last about 10 minutes per session, 9 sessions per week for up to 12 weeks, which will require up to 18 hours total.

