## **Statistical Analyses**

Prior to data analyses, the data collected under this study will be combined with data from its VA counterpart (IRB #2014-0939). Statistical analyses will be performed using this combined data set.

**Aim 1:** A repeated measures analysis model will be used to model changes in tongue strength in treatment and control groups, adjusted for age, gender, and baseline tongue strength. Each subject will have three observations: change between baseline and 8 weeks, baseline and 12

weeks, and 8 weeks and 12 weeks. This model will allow for comparison of differences between a) treatment durations (dose response) and b) between control and treatment groups.

**Aim 2:** Changes in oral intake and swallowing quality of life between baseline and 8 weeks, baseline and 12 weeks, and 8 weeks and 12 weeks will be modelled in a repeated measures analysis on treatment, adjusting for age, gender, and baseline outcome.

**Aim 3:** Change in number of new pneumonia diagnoses and number of hospital readmissions over a 1 year period, pre and post-study, will be modelled in linear regression models on treatment, adjusting for age, gender, and pre-study outcome.

All analyses will be performed on a randomized, or intention to treat basis, regardless of the actual treatment received. Study dropout by the subject will result in inclusion of incomplete data for that patient.

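### The Outcomes section makes device-tracked compliance a covariate, the Statistical Analyses section omits it; entered in the between-group models, it would replace the randomised group difference

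*Combined protocol and SAP*

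**What the plan says.** The Outcomes section, after listing the primary and secondary outcomes, adds: "Treatment compliance also will be tracked within the SwallowStrong® device and will serve as a covariate in statistical analyses". It names no model, no compliance measure and no value for control subjects.

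The Statistical Analyses section is where the models are written out. For Aim 1 it models change in tongue strength "in treatment and control groups, adjusted for age, gender, and baseline tongue strength". Aims 2 and 3 have parallel lists: age, gender, and the baseline outcome (Aim 2) or pre-study outcome (Aim 3). Compliance is in none of the three. The section then says: "All analyses will be performed on a randomized, or intention to treat basis, regardless of the actual treatment received".

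The Intervention section describes Group 1 as "a control group that will be receiving compensatory treatments only" and says of these subjects that "any type of lingual strengthening protocols specifically will be delayed until subjects have completed participation in this study". The take-home device is described only under Group 2. The Visits section gives the exercise load: "in Group 2, participation in the home exercises will last about 10 minutes per session, 9 sessions per week for up to 12 weeks". Under the Intervention section, a subject in either group who no longer meets the dysphagia criteria "on the 8-week videofluoroscopic swallowing examination, s/he will no longer continue participation in the study".

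**The concern.** The two sections give different covariate sets, and an analyst cannot follow both if the Outcomes sentence is taken to cover the Aim 1 to 3 models.

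The difference matters because of what compliance is. It is measured after randomisation, and controls do no device exercise, so they have no natural value. Adjusting for it does not change who is analysed, but in a between-group model it changes what is estimated. There are two obvious codings:

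- Controls missing: a complete-case fit contains no controls and cannot estimate a treatment effect. This would be noticed.
- Controls coded 0: the model runs without complaint, and the treatment coefficient becomes the expected difference between a Group 2 subject with zero compliance and a control.

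The second coding is the one to guard against, since the aims ask for the difference between the groups as randomised. The study is also meant to inform the sample size of a larger trial, so a between-group estimate that means something else could carry forward.

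**Working it through.** **Inputs from the documents** (Sample size calculation): 15 per group; SD of change 100 hPa in both groups; expected difference 100 − 20 = 80 hPa; alpha 0.05; two-sample t-test without covariates. Sidedness is not stated.

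**Assumed, because the documents give no compliance figures:** Group 2 compliance with mean m and SD s of 75% and 20%, or 60% and 30%, with 50%/35% and 90%/10% as outer cases; controls coded 0; a single change score per subject, as in Table 2.

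**Step 1: reproduce the plan's figure.** SE = 100 × √(2/15) = 36.5 hPa. The noncentral t with 28 df, two-sided, gives 75.3%, 56.2%, 35.5% and 18.5% for 100, 80, 60 and 40 hPa. Table 2 gives 75%, 56%, 35% and 18%, so it reproduces.

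**Step 2: what the coefficient becomes.** With all controls at 0, the compliance slope b is estimated from Group 2 alone. Least squares then gives

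treatment coefficient = (Group 2 mean − control mean) − b × m.

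The randomised difference is the first term only. If a share f of the 80 hPa is proportional to compliance, b × m = 80f on average, and the expected coefficient is 80(1 − f):

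- f = 0: 80 hPa
- f = 0.5: 40 hPa
- f = 1: 0 hPa

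The total effect is 80 hPa in all three. An independent simulation gave averages of about 80, 40 and 0. The identity needs no assumption about the compliance distribution.

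**Step 3: precision.** The extra term has variance 100² × m²/(14s²), so

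SE = 100 × √(2/15 + m²/(14s²)).

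- 75%, 20%: m²/(14s²) = 0.5625/0.56 = 1.0045; SE = 100 × √1.1378 = 106.7
- 60%, 30%: 0.36/1.26 = 0.2857; SE = 100 × √0.4190 = 64.7
- 50%, 35%: 0.25/1.715 = 0.1458; SE = 100 × √0.2791 = 52.8
- 90%, 10%: 0.81/0.14 = 5.7857; SE = 100 × √5.9190 = 243.3

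**Step 4: power of the treatment term** (noncentral t, 27 df, two-sided 0.05; residual SD held at 100 hPa).

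| Compliance mean, SD | SE (hPa) | f = 0 (80 hPa) | f = 0.5 (40 hPa) |
|---|---|---|---|
| Not in model | 36.5 | 56% | 56% |
| 75%, 20% | 106.7 | 11% | 6.5% |
| 60%, 30% | 64.7 | 22% | 9.2% |
| 50%, 35% | 52.8 | 31% | 11% |
| 90%, 10% | 243.3 | 6% | 5% |

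At f = 1 the expected coefficient is 0, and rejection is at the 5% level in every row with compliance in the model.

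**Step 5: the measure itself.** Nine sessions a week is 9 × 8 = 72 by week 8 and 9 × 12 = 108 by week 12. A subject who does every session and leaves at week 8 because dysphagia has resolved scores 72/72 = 100% or 72/108 = 67%, depending on a denominator the plan does not give.

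**The case against.** The strongest reply is that the harm depends on a model the documents do not write down. The Statistical Analyses section is the only place with models, its covariate lists are explicit, and an analyst who follows it estimates the intended contrast. The problem needs the general sentence in Outcomes to be read into those models, and controls to be coded 0. This stands, and it makes the consequence conditional. It does not remove the conflict: the Outcomes sentence is categorical, and nothing limits it to Group 2, where it would be harmless.

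Several stronger readings are tempting but not supported.

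- A reader might infer that the planned primary analysis is wrong. The models as listed omit compliance.
- A reader might infer that compliance belongs in the Aim 1 model because that model also addresses dose response. The text is "This model will allow for comparison of differences between a) treatment durations (dose response) and b) between control and treatment groups": dose there means treatment duration, 8 against 12 weeks, not sessions completed.
- A reader might infer that the week-8 exit rule biases the primary outcome through the denominator. The exit rule uses airway-invasion and residue scores, whereas the primary outcome is tongue pressure, and nothing says that those who leave gain more pressure. The missing denominator is only a gap in definition.
- A reader might infer that the choice will be made after the data are seen. The documents are silent on when it would be settled.

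The illustration can also be criticised for its spread (SE 53 to 243 hPa) and for using one change score, whereas Aim 1 has three per subject. Both criticisms are fair. The figures show direction and rough scale and do not predict a result.

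**Conclusion.** The point holds as a conflict between two sections with a conditional consequence. It is certain that Outcomes makes compliance a covariate, that the Aim 1 to 3 lists do not include it, and that no measure or control value is given. It is also certain, by algebra, that adding compliance with controls at 0 to a between-group model gives a contrast at zero compliance, which differs from the randomised difference whenever gain varies with compliance.

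The size rests on assumed compliance and on 15 per arm with SD 100 hPa. In the two main cases the standard error rises about 2.9-fold (106.7/36.5) or 1.8-fold (64.7/36.5). The quoted 11% and 22% power apply only if none of the gain runs through compliance. The 56% in the plan is correct for the test it describes, and neither it nor the sample size needs to change. This should be fixed because it bears on the primary comparison and costs almost nothing. Confidence is high for the conflict and the algebra; how likely the harm is depends on how the Outcomes sentence would be applied.

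**What to change.** Amend the compliance sentence in Outcomes to say that compliance is not a covariate in the between-group models for Aims 1 to 3, whose covariates remain those in Statistical Analyses. Report compliance descriptively. Examine any relation between compliance and outcome within Group 2 only, labelled exploratory, with compliance defined as sessions recorded divided by sessions scheduled while the subject was in the study (72 to week 8, 108 to week 12).

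The cost is one amended sentence, plus a one-line definition if the Group 2 analysis is kept. Data collection, sample size and Table 2 stay as they are.

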### **Data Reduction and Analysis**

*Videofluoroscopic Analysis:* The videofluoroscopic images will be coded and sent to the Speech Swallowing And Dining Enhancement (SSwal-ADE) Program. Clinicians blinded to subject information will obtain measures of bolus flow kinematics-direction (Penetration/Aspiration Scale scores), duration, and completeness (Residue Scale scores) from fluoroscopic recordings for each subject using Adobe Premier Pro software. Visual perceptual review will be performed by judges viewing each swallow at normal, slowed, and frame-by-frame speeds as often as needed for confident judgments. Twenty percent of the swallows will be chosen randomly and re-measured by the same judge and a different judge (one of the experienced UW SLPs) to assess inter and intra-judge reliability for all variables. Bolus flow durational measurements (oral transit time, stage transit duration, pharyngeal transit time, total swallow duration) will quantify timing of structural movement and bolus flow. *Computational analysis of swallowing mechanism (CASM) will be performed in order to track anatomical coordinates during the swallow. This will allow us to quantify displacement of various swallowing related structures.*

*Pressure Analysis:* Maximum isometric and swallowing pressures and their temporal characteristics (i.e., rise rate) will be quantified using the SwallowSTRONG® device and the DSW. Swallowing pressures will be quantified relative to the videofluoroscopic images to ensure that the pressure being measured is relevant to bolus flow and not bolus manipulation prior to the swallow. Twenty percent of the pressure wave forms will be chosen randomly and re-measured by the same judge and a different judge to assess inter- and intra-judge reliability.

*Swal-QOL:* Responses will be extracted and scored for subsequent statistical analysis using a database scoring program. All of the Swal-QOL scales will be scored by using Likert's methods of summated ratings.

*Saliva Analyses:* Each measure of viscoelasticity and lubrication properties will be recorded three times per sample. Apparent viscosity will be determined using a TA Discovery, HR-2 rheometer (TA Instruments, New Castle, DE, USA) equipped with a Peltier plate temperature control unit (233212.902). All measurements will be carried out with a flat plate geometry with a diameter of 20 mm and an operating gap of 200 µm. Each sample will first be allowed to equilibrate for 30 seconds at 37°C on the rheometer stage. Viscosity will then be measured at 37°C at shear rates ranging from 0.1 to 100 1/s. In [name] laboratory, samples will be frozen until all have been collected. Then, an enzyme-linked immunosorbent assay (ELISA) will be completed in order to quantify levels of the protein Substance P within the samples.

**Hospital Readmissions and Pneumonia Diagnoses:** The number of pneumonia diagnoses and overall hospital readmissions will be compared for the same period of time prior to enrollment and following completion of the study (up to 9 months) for each subject. Discharge reports will be used to tally the number of readmissions and clinic notes will be reviewed to determine number of pneumonia diagnoses (community, hospital-acquired, and aspiration pneumonia) for each subject.

### **Study Timeline**

We estimate achieving our target enrollment in 9 months and completion of the project within the specified 12-month period as outlined below in Table 1. Patients will be referred from the UWHC Neurology Department where approximately 500 ischemic stroke patients are seen yearly. This large volume of patients ensures that 40 subjects will be easily accessible for recruitment into the proposed study.

Tasks	1/1/2015-12/31/2015			
	Q1	Q2	Q3	Q4
Database build & training of study staff	→			
Subject enrollment	→	→	→	
Study close out, data analysis				→

### **Data Safety and Monitoring**

During visits for study participation, subjects will be accompanied by study personnel at all times. Subjects will be contacted by study staff weekly to assess for unanticipated problems or complications. If an unanticipated problem takes place, study personnel will be immediately aware and will take action (i.e., request medical support). As this is a low risk study, adverse events are expected to be very rare. Any unanticipated problems will be reported to the IRB according to posted guidance. Subjects will also have a study contact number and be encouraged to contact study staff with their questions or concerns. Throughout the study, we will notify participants of new information that may become available and might affect their decision to remain in the study.

There are no known social, legal, psychological, or financial risks associated with participation.

***Confidentiality:*** Breach of confidentiality is possible, but not likely because of safeguards in place. The procedures for protecting the participants' confidentiality are in place. All participants will sign the informed consent document prior to participating in the study. All paper documents will be locked in a filing cabinet in a secure room within the University of Wisconsin-Madison's Department of Medicine UW Speech, Swallowing, and Dining Enhancement (SSWAL-ADE) laboratory and only study staff will have access to that cabinet. All electronic files related to data will be password protected and stored on a password-protected hospital network. Once enrolled, each subject will be assigned a code number crossing over to the private health information (PHI) gathered from his/her medical record, and all data gathered under the research

protocols will be recorded only by this code number. The link connecting the subject and code number will be password-protected stored separately in electronic format on the password-protected hospital network and only the PI ([name]) will have access. Only the approved project research staff ([name], [name]) will have access to the coded study data. All information about the subject will be treated confidentially and will not be revealed unless required by law. All HIPAA regulations pertaining to protection of participants and eliminating identification will be followed. Data will be de-identified at the close of the study. Any breach of confidentiality will immediately be reported to the IRB. Individual medical records will be accessed twice during the one year duration of this study: once by [name] initially to confirm the subjects' eligibility for the study and then again at the end of the study (one year point) to determine number of pneumonia diagnoses and hospital readmissions for the same number of months pre- and post-enrollment. Results of study-related procedures performed solely for research purposes (not standard of care) will not be placed in the subjects' medical record.

*Videofluoroscopic Swallowing Assessment:* Subjects are at risk for aspirating during the VFS assessment. If aspiration occurs during the VFS assessment, the particular bolus condition will be terminated once the cause of the aspiration is determined. Following completion of the study protocol, compensatory approaches to treatment (e.g., postures, diet modification) may be attempted in order to determine which strategies are most effective in reducing or eliminating the occurrence of airway penetration and/or aspiration, thereby ensuring safety with swallowing for patients in both treatment groups.

Subjects will be exposed to radiation exposure equivalent to one to two years of background radiation (less than 2.5 minutes) during the videofluoroscopic swallowing study. The risks of that amount are considered to be very small, and there is no indication of harmful effects to an individual. Subjects will not be included if they are pregnant. Radiation exposure during the VFS assessment will be limited as much as possible through attention to time restraints and adherence to ASHA's Guidelines for Speech-Language Pathologists Performing Videofluoroscopic Studies. Protective apparel with lead-shielding (lead apron, thyroid shield) will be worn at all times.

*Muscle Soreness:* Subjects who report muscle soreness during the treatment protocol will be offered breaks throughout treatment sessions if needed.

*Abstaining from strengthening approaches to dysphagia treatment in the acute post-stroke phase of recovery:* There may be unknown risks for subjects randomized to Group 1 who will be abstaining from strengthening approaches for the treatment of dysphagia that might be included as part of standard care. As there is not a clear standard regarding strengthening approaches for dysphagia rehabilitation post-stroke, it is unclear if omission of these approaches will result in adverse effects.

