This initial work supports the potential of this therapy approach to affect health-related outcomes in addition to swallowing-specific outcomes in a variety of patient groups. However, the efficacy of SwallowSTRONG® DF I-PRO therapy for treating dysphagia and overall health status in patients post-stroke has yet to be established in a larger, more homogeneous group of subjects and with comparison to a control group.

*Salivary Analyses:* A decrease in ratings of mouth dryness has also been observed in patients enrolled in the VA Clinical Demonstration Program previously referred to. The reason for this decrease in mouth dryness is unclear. Additionally, levels of substance P, a protein in saliva, have been shown to be related to the occurrence of silent aspiration in patients post-stroke. Some preliminary data have shown that intraoral stimulation may increase levels of substance P. Stimulation of the salivary glands provided by repeated lingual presses may have the same outcome. Analyses of salivary flow rate as well as the quality of saliva will be important in more clearly understanding these observed changes in this group of patients post-stroke.

*Dose Response:* In order to encourage optimal outcomes of SwallowSTRONG® DF I-PRO therapy, while simultaneously considering patient tolerance and compliance, knowledge of ideal treatment duration is critical. In previous work, DF I-PRO therapy has been implemented as an 8 week program; however, acute and chronic post-stroke patients have continued to demonstrate improvement at completion of the program. This suggests that a subset of patients may benefit from a longer protocol (dose).

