**Group 2: SwallowSTRONG® device-facilitated I-PRO therapy plus compensatory treatments:**

[figure not shown]
Isometric tongue strengthening will be completed using the SwallowSTRONG® device (see Figure 1).

This device hand-held instrument provides numeric readout of pressure (hPa) and digital feedback of performance. It consists of a short cord (approx. 10 inches), which is attached to a small digital touch screen display. The 4-sensor array is custom-molded to the hard palate to ensure consistent placement.

Tongue press exercises consist of pressing the tongue against the sensors. Isometric exercises will focus on the anterior and posterior sensor. Subjects will be given a target pressure value for both the anterior and posterior sensor locations for which to aim during strengthening. Visual feedback on the display will signal the subject that they have attained their target pressure goal.

Prior to initiation of the strengthening regimen, baseline one repetition maximum (1RM) lingual pressures will be obtained at the anterior and posterior sensors independently by gathering 3 tongue press trials at each site that differ by less than 5% to adjust for variability in these measures. Subjects will take the SwallowStrong® device home with them and will complete 20 repetitions of the exercise (10 repetitions at the front sensor; 10 repetitions at the back sensor), three times per day on three days per week for twelve weeks. It will take approximately 10 minutes to complete 20 repetitions of the exercise resulting in about 30 minutes total for each home exercise session. During week one of the regimen, the target value of each repetition will be 60% of the 1RM. For the remaining eleven weeks of the program, the target value will be increased to 80% of the 1RM. These values of 60% and 80% were chosen based on previous work that employed progressive resistance training for the limbs and lingual musculature with healthy elders and patients post-stroke. At weeks three, five, seven, nine, and eleven, the baseline will be re-measured by phone and the 80% target value re-calculated. In addition, check-in phone calls also will be scheduled the other weeks of the study period.

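### Muscle soreness is the one risk tied to the exercise, yet no recording or summary of it is planned, so 8 and 12 weeks would be compared on benefit alone

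*Combined protocol and SAP*

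**What the plan says.** Data Safety and Monitoring lists the study's risks. The only one that comes from the strengthening exercise is muscle soreness, and the provision for it is "Subjects who report muscle soreness during the treatment protocol will be offered breaks throughout treatment sessions if needed". The other entries concern confidentiality, aspiration and radiation at videofluoroscopy, and Group 1's abstention from strengthening. The same section also says "Subjects will be contacted by study staff weekly to assess for unanticipated problems or complications".

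The Group 2 description places the exercise at home: "Subjects will take the SwallowStrong® device home with them and will complete 20 repetitions of the exercise".

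In Background and Significance, the Dose Response paragraph says that, "while simultaneously considering patient tolerance and compliance, knowledge of ideal treatment duration is critical". Hypotheses 1b and 2b then predict that 12 weeks will do better than 8.

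Outcomes lists lingual pressure as primary. It adds bolus-flow durations, swallowing pressures, SWAL-QOL, FOIS, pneumonia diagnoses and readmissions. On adherence it says "Treatment compliance also will be tracked within the SwallowStrong® device and will serve as a covariate in statistical analyses". Statistical Analyses describes models for Aims 1 to 3 and nothing else.

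**The concern.** The protocol says that tolerance should be weighed with duration, and it names one way in which the exercise might be poorly tolerated. It then plans no result that would show how well the exercise was tolerated. The duration comparison covers pressure, bolus flow, oral intake and quality of life only.

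The stake is practical. The pilot is meant to inform a larger trial. If 12 weeks looks better than 8 on strength, readers will want to know how many treated subjects were sore and whether soreness appeared or persisted in the added four weeks. If the calls do not record this at the time, it cannot be reliably recovered at analysis. The planned medical-record review looks for pneumonia and readmissions, and the dropout statement calls for incomplete data to be included without asking why a subject left.

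**Working it through.** **1. Does any planned element already supply the result?**

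- *Outcomes:* no soreness, adverse-event or tolerability measure is listed.
- *Statistical Analyses:* Aim 1 models change in tongue strength, Aim 2 oral intake and quality of life, and Aim 3 pneumonia and readmissions. There is no safety table.
- *Weekly contact:* Group 1 has weekly check-in calls. Group 2 has re-measurement calls at weeks 3, 5, 7, 9 and 11 and check-in calls in the other weeks. Both arms can therefore be asked. No soreness item, grading, denominator or summary is specified.
- *Compliance:* the device logs it, and Outcomes makes it a covariate. The Aim 1 and Aim 2 models list age, gender and the baseline value; Aim 3 lists age, gender and the pre-study outcome. Compliance is in none of them. It can show that sessions were missed, but not why.

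No planned result describes soreness or adverse events.

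**2. Who can be observed in each period?** Under Intervention, a subject whose dysphagia has resolved at the 8-week videofluoroscopy leaves the study. Weeks 9-12 are therefore seen only in those who continue, and a summary needs a separate denominator for that period.

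**3. What could the pilot estimate?** The protocol gives no soreness rate, so there is no stated figure to reproduce on this point. The input is 15 subjects per group, from the sample size section. That section's power figures do reproduce (two-sided two-sample t-test, 15 per group, SD 100 hPa, difference 80 hPa: 56.2% against the stated 56%), and recording soreness does not alter them.

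For no cases in n subjects, the exact (Clopper-Pearson) two-sided 95% upper limit is 1 − 0.025^(1/n):

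- n = 15: 1 − 0.025^(1/15) = 21.8%
- n = 10 (an assumed number continuing past week 8): 1 − 0.025^(1/10) = 30.8%

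Exact 95% intervals for other illustrative counts:

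- 3 of 15 (20%): 4.3% to 48.1%
- 5 of 15 (33%): 11.8% to 61.6%

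The chance of at least one case among 15 is 1 − (1 − p)^15. The true rates p are assumptions:

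| Assumed true rate | Chance of at least one case |
|---|---|
| 5% | 54% |
| 10% | 79% |
| 20% | 96.5% |
| 30% | 99.5% |

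If soreness were common, the pilot would very probably see it. It could not estimate the rate closely, and it could not exclude a sizeable rate if no case were seen.

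**The case against.** The best defence is that monitoring exists. Staff call every week, the call wording can be read to include any complication, anticipated or not, and the soreness provision itself assumes that subjects will report it. Compliance is objective and bears directly on whether patients sustain 12 weeks. The study is a pilot whose stated use is to size a larger trial, and no Aim 1-3 estimate, test or power figure changes. All of this stands. It limits the point to recording and reporting; it does not supply either.

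A reader might be tempted to go further in five ways that the text does not support:

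- *That the soreness provision contradicts home exercise.* An offer of breaks could be made at the baseline training, on a call or through the study contact number. How breaks apply at home is unspecified, which is a gap and not a conflict.
- *That soreness falls outside monitoring because it is anticipated.* The call wording is open to either reading.
- *That the choice of duration depends on tolerability.* The background asks for tolerance and compliance to be considered, and no section sets a rule for choosing 12 weeks over 8.
- *That soreness is an established harm of this therapy.* The protocol gives no rate, severity or evidence for it.
- *That the pilot would wrongly claim safety.* "As this is a low risk study, adverse events are expected to be very rare" is an expectation stated in a monitoring section. It is not a result the study sets out to show.

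Nor would the number of exercise repetitions measure the problem, since it says nothing about how often soreness occurs.

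**Conclusion.** The point holds as a gap in data collection and reporting. The one exercise-specific risk has no planned recording or summary, although the protocol's own rationale puts tolerance beside duration. The 8- versus 12-week comparison would therefore be reported on benefit alone, with compliance as a partial proxy that the described models omit.

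Its size is modest. No efficacy analysis is affected, and 15 treated subjects give only a wide interval (upper limit 21.8% even with no cases). The gap is still worth closing, because the information has to be collected as the calls are made. The precision figures assume 15 treated subjects with data. The rates of 5% to 30% and the 10 subjects continuing past week 8 are illustrations, because the documents give neither.

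**What to change.** - On the weekly calls already scheduled in both arms, record new or continuing soreness and any other complication, anticipated or not.
- Add to Outcomes and Statistical Analyses a descriptive table by arm: number and percentage of subjects with soreness, and with any adverse event, with exact 95% intervals.
- For Group 2, show weeks 1-8 and weeks 9-12 separately, with the later denominator limited to those who continue past the 8-week visit. Place this beside device-logged compliance and report it with the duration comparison.
- Clarify how the breaks described under Data Safety and Monitoring apply to sessions done at home. No clinical rule is proposed here.

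The cost is one item on an existing call and one table. The downside is that subjects know their arm, so self-reported soreness may differ between arms for that reason alone. With the wide intervals as well, the table should stay descriptive, without a between-arm test.
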